#### **Prior EPA (fish oil) study by our team in advanced cancer patients:**

Our team conducted a study in 60 advanced cancer patients with decreased weight and appetite who were randomly assigned to fish oil capsules or placebo (daily dose of 18 gelatin capsules containing either 1,000 mg of fish oil (Marine Lipid Concentrate Capsule [Banner Pharmacaps, Halifax, Canada] containing 180 mg of EPA, 120 mg of docosahexaenoic acid [DHA], and 1 mg of vitamin E) or 1,000 mg of a placebo (olive oil). Appetite, tiredness, nausea, well-being, caloric intake, nutritional status, and function were prospectively assessed at days 1 and 14. Fish oil did not significantly influence appetite, tiredness, nausea, well-being, caloric intake, nutritional status, or function after 2 weeks compared with placebo in patients with advanced cancer and loss of both weight and appetite. The tiredness or fatigue improved significantly ( $p= 0.04$ ) in patients who received higher dosage (Table 1). However the dose (1.8gm of EPA, short duration of treatment (2 weeks), number of capsules, and no validated measure for fatigue were the limitations of this study.

**Table 1. Differences between Placebo and Fish Oil group at Baseline and Day 14**

Variable*	Placebo† (n = 30)	P†	Fish Oil† (n = 30)	Correlation‡ with Dose	
				r	p
Appetite VAS, 0–100 mm	−9.0 ± 27	NS	−9.8 ± 20	0.15	NS
Tiredness VAS, 0–100 mm	4.2 ± 33	.19	−5.5 ± 22	0.38	.04
Nausea VAS, 0–100 mm	0.5 ± 37	NS	−5.2 ± 22	−0.28	.13
Overall well-being VAS, 0–100 mm	−9.8 ± 32	NS	−4.6 ± 20	0.08	NS
Weight, kg	−0.89 ± 3.8	NS	0.03 ± 2.8	0.008	NS
Caloric intake, kcal	−57 ± 1299	NS	51 ± 1177	−0.06	NS
KPS, score, 0–100	−6.9 ± 10	NS	0.0 ± 8	−0.19	NS
EFAT, score, 0–30	0.2 ± 2	NS	0.3 ± 3	0.04	NS

\*Data are shown as the mean ± SD and report the difference between day 14 and baseline (negative numbers denote improvement in VAS).

†Differences in the fish oil and placebo group, respectively.

‡Pearson's correlation between the number of capsules taken and the variable (fish oil group only).

**Prior PA Studies by our team:**

Prior studies led by [name] tested interventions in patients with highly symptomatic prostate cancer (TPRB-98-103-01-PBP), mCRC, and in breast cancer (CA89519). The breast cancer study showed improved 6-minute walk performance and QOL. In an R01-funded study of PA in endometrial cancer survivors, the intervention was completed with a high percentage and was well received among the participants. The same methods will be used in the proposed study. In the next few months, a 154 person trial comparing a home-based PA intervention to a relaxation intervention for improving physical functioning and managing symptoms in advanced colorectal cancer patients (R21 CA137333) will be completed. To date only 5 patients in the PA arm have experienced adverse events (AE; 9 AE total, 1 definitely attributable to physical activity, 8 possibly attributable. All AE were grade 1 (5) or grade 2 (4). None of the AEs were due to falls.

An ongoing study in highly symptomatic prostate cancer patients, NCT01410942, conducted by the same team as that in the proposed study (PI: [name]; [name] (Co-I), uses the same standardized exercise regimen in combination with study drug. Table 2 shows the adherence rates and safety data of the first 12 patients enrolled (blinded). The enrolled patients in this ongoing study had no difficulty in completing all the assessments. Based on the preliminary data presented, we conclude that this proposed PA would be feasible and safe.

**Prior Inflammatory cytokine and CRF studies by our team:**

Prior studies by our group showed wide variability in serum cytokine levels in patients with advanced cancer and hence the need to assess cytokines levels in LPS activated monocytes. PA results in modulation of TNF- $\alpha$ , IL-1 $\beta$ , and IL-6, interleukin-1 receptor antagonist (IL-1RA), TNF-receptors (TNF-R), and IL-10 levels. Since most of these factors are produced by activated monocytes/macrophages, we propose to assess the synthesis of these factors by resting (unstimulated) as well as LPS-activated peripheral blood monocytes isolated from patients before and after study treatment.

Figure 2 shows the synthesis of TNF- $\alpha$  by LPS-activated monocytes isolated from patients at baseline (D0) and at weeks 1- 5 after treatment with dexamethasone (DM). In patients treated with 8 mg DM daily (dark histograms), the percentage of LPS-activated monocytes that synthesized TNF- $\alpha$  decreased, whereas in patients receiving placebo (light histograms) for the first 2 weeks there was no change in the percentage of LPS-activated monocytes that synthesized TNF- $\alpha$  from D0 until week 2. Thereafter, when placebo patients (light histograms) switched to open-label DM, there was a decrease in the percentage of LPS-activated monocytes that synthesized TNF- $\alpha$ . Hence analyses of the levels of cytokines from induced monocytes would help to determine their association with change CRF and treatment, as shown in our previous studies.

**Change in TNF- $\alpha$  production by LPS-activated monocytes from dexamethasone-treated patients and placebo-treated patients in double-blind phase (Days 8 and 15) and in dexamethasone-only open-label phase (Days 29 and 35).**

**Figure 2. Monocyte Phenotype and LPS-induced cytokine synthesis.** (A) Monocytes are enumerated in whole blood as CD14\*SSCmid cells. (B) After a 4 hour incubation with LPS, the percentage of cell synthesizing cytokines can be enumerated. (C) TNF- $\alpha$  synthesis by monocytes decreases in patients treated with 8mg dexamethasone daily.

## 2. Study objectives

**Primary Objective:** 1. To determine the effects of the combination of Icosapent ethyl 2 gm orally daily plus PA for the reduction of cancer related fatigue [FACT-F subscale] at the end of 8 weeks in patients with advanced cancer by comparing the difference between the FACT-F subscale score at baseline and at 57±5 days, between patients who will receive either Icosapent ethyl plus PA or placebo plus physical activity.

### Secondary Objectives:

1. To determine the feasibility, adherence, and satisfaction of using the combined intervention for the reduction of cancer related fatigue in patients with advanced cancer.

2. To explore the effects of the combination of Icosapent ethyl 2 gm orally daily plus PA on quality of life-related variables, mood (HADS – Hospital Anxiety and Depression Inventory), quality of life domains (FACT-G), Cancer related Symptoms (Edmonton Symptom Assessment Scale – ESAS) in these patients.
3. To explore the effects of combined intervention on serum C - reactive protein and intracellular cytokine levels [IL-6, TNF- $\alpha$ , IL-10, IL-1RA] before and after treatment.
4. To explore its side effects and tolerability of the combined study interventions in these patients.
5. To explore the effect of multimodal therapy on body composition.
6. To explore the effect of the proposed treatment in this study on the overall survival time in patients

We hypothesize that:

- The combination of Icosapent ethyl plus PA is capable of significantly reducing the severity of CRF between baseline and end of week 8 [FACT-F subscale].
- Physical activity is capable of reducing the severity of CRF between baseline and end of week 8.

### **4. Study Design**

#### **4.1 Study population**

Patients with advanced cancer will be recruited from UTMDACC. At UTMDACC, patients will be recruited from medical oncologists working in outpatient clinics, and in our own outpatient supportive care center. Patients will be screened for eligibility criteria. Patients who are eligible and who provide written informed consent to participate in this research study will be admitted to the double-blind phase of the study described below. Consent forms and assessments will be available and administered by the study-assigned research nurse. Feasibility: Is based on the prior successful accrual in similar symptom control trials by our group in these sites and great interest in Complementary and Alternative Medicine (CAM) in this population (48%).

### **5. Eligibility**

#### **5.1.1 Inclusion criteria**

**Inclusion Criteria:**

- a) Diagnosis of advanced cancer
- b) Patients should describe fatigue as being present for a minimum of 2 weeks;
- c) Patients should rate the severity of fatigue as 4/10 in a 0-10 ESAS scale, where 0=no fatigue, 10=worse fatigue possible;
- d) If patients are on opioids for the treatment of cancer pain, they must have had no major dose change (>25%) for at least 48 hours prior to study entry. Change in opioid dose after study entry is allowed;
- e) Presence of relatively intact cognition defined by normal memorial delirium assessment scale (<7/30); sign written informed consent;
- f) Patients must be 18 years or older. The questionnaires used in this study have been validated only in the adult population;
- g) Patient willing to keep a daily diary, engage in telephone follow up with a nurse;
- h) Patient must have telephone access to be contacted by the research nurse;
- i) Hemoglobin of  $>/= 10$  g/dl within 2 weeks of enrollment. If the patient has not had blood drawn for a hemoglobin level in the past two weeks, one will be done to determine the eligibility.
- j) Patients should have a Zubrod  $</= 1$ .
- k) Life expectancy of  $>/= 4$  months.
- l) Subjects must be able to understand and be willing to sign the written informed consent form. A signed informed consent form must be appropriately obtained prior to the conduct of any trial-specific procedure.
- m) Adequate bone marrow, liver and renal function as assessed by the following laboratory requirements:
  - Total bilirubin  $\leq 1.5 \times$  the upper limits of normal (ULN)
  - Alanine aminotransferase (ALT) and aspartate amino-transferease (AST)  $\leq 2.5 \times$  ULN ( $\leq 5 \times$  ULN for subjects with liver involvement of their cancer)
  - Alkaline phosphastase limit  $\leq 2.5 \times$  ULN ( $\leq 5 \times$  ULN for subjects with liver involvement of their cancer)
  - Serum creatinine  $\leq 1.5 \times$  the ULN
  - International normalized ratio (INR)/ Partial thromboplastin time (PTT)  $\leq 1.5 \times$  ULN. (Subjects who are prophylactically treated with an agent such as warfarin or heparin will be allowed to participate provided that no prior evidence of underlying abnormality in coagulation parameters

exists. Close monitoring of at least weekly evaluations will be performed until INR/PTT is stable based on a measurement that is pre-dose as defined by the local standard of care. (See Section 3.3)

- Platelet count > 100000 /mm^3, hemoglobin (Hb) >/= 10 g/dL, absolute neutrophil count (ANC) 1500/mm^3. Blood transfusion to meet the inclusion criteria will not be allowed.

n) Women of childbearing potential must have a negative serum pregnancy test performed within 7 days prior to the start of study drug. Post-menopausal women (defined as no menses for at least 1 year) and surgically sterilized women are not required to undergo a pregnancy test. The definition of adequate contraception will be based on the judgment of the investigator.

o) Subjects (men and women) of childbearing potential must agree to use adequate contraception beginning at the signing of the ICF until at least 2 months after the last dose of study drug. The definition of adequate contraception will be based on the judgment of the principal investigator or a designated associate.

p) Subject must be able to swallow and retain oral medication.

q) Patients on pain medications (non-opioids), including NSAIDS and acetaminophen, may be enrolled as long as they have been using it chronically, at least more than 2 weeks.

### **5.1.2 Exclusion criteria**

#### **Exclusion Criteria:**

a) Major contraindication to fish oil i.e. hypersensitivity to fish/ fish oil or physical activity;

b) Currently on fish oil or has been on fish oil within the last 10 days;

c) Inability to complete the baseline assessment forms or to understand the recommendations for participation in the study.

d) Pregnant or lactating women. Childbearing age women are not on birth control.

e) Reports a falls in the past 30 days;

f) Patient reported regular participation in moderate- or vigorous-intensity PA for at  $\geq$ 30 minutes at least 5 times a week and strength training for  $\geq$ 2 days/week;

g) Signs of third spacing as determined by the treating physician (e.g., pedal edema, pleural effusion, ascites)

h) Previous assignment to treatment during this study. Subjects permanently withdrawn from study participation will not be allowed to re-enter study.

i) Uncontrolled hypertension (systolic pressure >140 mm Hg or diastolic pressure > 90 mm Hg [NCI-CTCAE v4.0] on repeated measurement) despite optimal medical management.

j) Active or clinically significant cardiac disease including:

- Congestive heart failure – New York Heart Association (NYHA) > Class II.
- Active coronary artery disease.
- Cardiac arrhythmias requiring anti-arrhythmic therapy other than beta blockers or digoxin.
- Unstable angina (anginal symptoms at rest), new-onset angina within 3 months before randomization, or myocardial infarction within 6 months before randomization.

k) Evidence or history of bleeding diathesis or coagulopathy.

l) Any hemorrhage or bleeding event  $\geq$  NCI CTCAE Grade 3 within 4 weeks prior to start of study medication.

m) Subjects with thrombotic, embolic, venous, or arterial events, such as cerebrovascular accident (including transient ischemic attacks) deep vein thrombosis or pulmonary embolism within 6 months of start of study treatment within 6 months of informed consent.

n) Patients with any previously untreated or concurrent cancer that is distinct in primary site or histology except cervical cancer in-situ, treated ductal carcinoma in situ of the breast, curatively treated nonmelanoma skin carcinoma, noninvasive aerodigestive neoplasms, or superficial bladder tumor. Subjects surviving a cancer that was curatively treated and without evidence of disease for more than 3 years before registration are allowed. All cancer treatments must be completed at least 3 years prior to registration.

o) Patients with phaeochromocytoma.

p) Known history of human immunodeficiency virus (HIV) infection or current chronic or active hepatitis B or C infection requiring treatment with antiviral therapy.

q) Ongoing infection  $>$  Grade 2 NCI-CTCAE v4.0.

r) Symptomatic metastatic brain or meningeal tumors.

s) Presence of a non-healing wound, non-healing ulcer, or bone fracture.

t) Major surgical procedure or significant traumatic injury within 28 days before start of study medication

u) Renal failure requiring hemo- or peritoneal dialysis.

v) Dehydration Grade >1 NCI-CTCAE v4.0.

w) Patients with seizure disorder requiring medication.

x) History of Persistent proteinuria

CTCAE v4.0 NCI

y) Interstitial lung disease with ongoing signs and symptoms at the time of informed consent.

z) Pleural effusion or ascites that causes respiratory compromise ( $\geq$  NCI-CTCAE version 4.0 Grade 2 dyspnea).

aa) History of organ allograft (including corneal transplant).

bb) Known or suspected allergy or hypersensitivity to any of the study drugs, study drug classes, or excipients of the formulations given during the course of this trial.

cc) Any malabsorption condition.

dd) Women who are pregnant or breast-feeding.

ee) Any condition which, in the investigator's opinion, makes the subject unsuitable for trial participation.

ff) Substance abuse, medical, psychological or social conditions that may interfere with the subject's participation in the study or evaluation of the study results.

### 5.1.3 Excluded therapies and medications, previous and concomitant

- Concurrent use of another investigational drug or device therapy (i.e., outside of study treatment) during, or within 4 weeks of trial entry (signing of the informed consent form).
- Major surgical procedure, open biopsy, or significant traumatic injury within 28 days before start of study medication.
- Therapeutic anticoagulation with Vitamin-K antagonists (e.g., warfarin) or with heparins and heparinoids.
- - However, prophylactic anticoagulation as described below is allowed:
    - Low dose warfarin (1 mg orally, once daily) with PT-INR  $\leq$  1.5 x ULN is permitted. We will monitor the PT/INR weekly for patients on warfarin and liver function test every 2 weeks (Total bilirubin, and AST (SGOT) and ALT (SGPT) if hepatic metastases are present or if patients are on potentially hepatotoxic agents such as acetaminophen or statins.
    - Low dose aspirin  $\leq$  100 mg daily).
    - Prophylactic doses of heparin.
- Use of any herbal remedy (e.g. St. John's wort [Hypericum perforatum])
- Use of Dexamethasone for cancer related fatigue

## 5.2 Withdrawal of subjects from study

### 5.2.1 Withdrawal

Subjects **must be withdrawn from the trial** (treatment and procedures) for the following reasons:

- Subject withdraws consent from study treatment and study procedures. A subject must be removed from the trial at his/her own request or at the request of his/her legally acceptable representative. At any time during the trial and without giving reasons, a subject may decline to participate further. The subject will not suffer any disadvantage as a result.
- Pregnancy. Pregnancy will be reported as an SAE. (Note: subjects who have been withdrawn from treatment with study drug because of pregnancy should not undergo CT scans [with contrast]/MRI or bone scans while pregnant.)
- If, in the investigator's opinion, continuation of the trial would be harmful to the subject's well-being.
- Subject is lost to follow-up.
- Death.

Subjects **may be** withdrawn from the study for the following reasons:

- The subject is non-compliant with study drug, trial procedures, or both; including the use of anti-cancer therapy not prescribed by the study protocol.
- Severe allergic reaction to fish oil.
- The development of a second cancer.
- Development of an intercurrent illness or situation which would, in the judgment of the investigator, significantly affect assessments of clinical status and trial endpoints.
- Deterioration of ECOG performance status to 4.
- Use of illicit drugs or other substances that may, in the opinion of the investigator, have a reasonable chance of contributing to toxicity or otherwise skewing trial result.

Any subject removed from the trial will remain under medical supervision until discharge or transfer is medically acceptable.

In all cases, the reason for withdrawal must be recorded in the CRF and in the subject's medical records. Details for the premature termination of the study as a whole (or components thereof [e.g. centers, treatment arms, dose steps]) are provided in Section 10 ( Premature termination of the study).

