### **5.2.3 Replacement**

No withdrawn subjects will be replaced.

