#### **Treatment compliance**

An adequate record of receipt, distribution, and return of all study drugs (Icosapent Ethyl/Placebo) must be kept in the form of a Drug Accountability Form.

Subject compliance with the treatment and protocol includes willingness to comply with all aspects of the protocol, and to have blood collected for all safety evaluations. At the discretion of the principal investigator, a subject may be discontinued from the trial for non-compliance with follow-up visits or study drug.

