This study is considered feasible if patient is adherent to the study. Adherence will be calculated as the mean of the percentage of total prescribed strength training sessions, the percentage of total prescribed walking regimen minutes completed (PA), and the mean (across all patients) percentage of total prescribed pills taken (study medication). The adherence rate, as defined, is a continuous variable. At the end of the study, we will estimate the average adherence of prescribed strength, of total prescribed walking regimen minutes and of total prescribed pills taken separately using mean, standard deviation, median, and range. This study intervention of combination of Icosapent Ethyl and Physical activity will be considered feasible as evidenced by adherence rate is  $>/=75\%$  to daily combined therapy during the 8-week intervention. The adherence rate can also be compared among all three groups using Kruskal-Wallis test. We will estimate 95% confidence intervals for the proportion of patients completing the intervention, the adherence rate, and the proportion of patients with a satisfaction over time. With 30 patients in each arm, a 95% confidence interval for a proportion of 73% (22/30), for example, can be estimated as (54%, 88%).

Data of variables of interest will be summarized using standard descriptive statistics, such as mean, standard deviation, median, and range for continuous variables, frequency and proportion for categorical variables. Correlation will be assessed among continuous variables using Pearson or Spearman correlation coefficient, whichever is appropriate. Association between categorical variables will be examined by Chi-Squared test or Fisher's exact test when appropriate. Boxplot and histogram will be applied to demonstrate distribution of variables of interest.

Since FACIT-F scores will be obtained at 0, 15, 29, 43 and  $57\pm 5$  days, and other QOL variables and cytokine markers will also be obtained repeatedly over time, we will also evaluate the effect of treatment on the changes of these measured over time using repeated measure analysis in which intra-

patient correlation of the measures are accounted for. However due to the small scale and exploratory nature of the study, we will report p-value as is without adjusting for multiplicity.

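### Non-compliance can end study participation at discretion, and nothing keeps the Day 57 FACIT-F going afterwards, so primary scores may be lost from patients who could still give them

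*Combined protocol and SAP*

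**What the plan says.** Section 5.2.1 has two lists. The mandatory list (consent withdrawn, pregnancy, harm in the investigator's opinion, loss to follow-up, death) defines trial withdrawal as covering both treatment and procedures. The optional list concerns withdrawal from the study and includes "The subject is non-compliant with study drug, trial procedures, or both; including the use of anti-cancer therapy not prescribed by the study protocol". The Treatment compliance paragraph after Section 6.6 adds: "At the discretion of the principal investigator, a subject may be discontinued from the trial for non-compliance with follow-up visits or study drug". Neither place gives a threshold.

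After removal, Section 5.2.1 provides for medical supervision and for documentation: "In all cases, the reason for withdrawal must be recorded in the CRF". It mentions no further questionnaire. Section 5.2.2 classes anyone who leaves early after randomisation as a dropout, and Section 5.2.3 states: "No withdrawn subjects will be replaced".

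Section 8 tests the change in FACIT-F from baseline to Day 57 between the two physical-activity arms by t-test. It defines no efficacy analysis population. Multiple imputation is optional, and a repeated-measures analysis of FACIT-F is additional.

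On feasibility, Section 8 says the combination "will be considered feasible as evidenced by adherence rate is" at least 75% over the 8-week intervention. The pill component of adherence reads "and the mean (across all patients) percentage of total prescribed pills taken (study medication"; the strength and walking components carry no such qualifier. Section 8 also says: "The adherence rate can also be compared among all three groups using Kruskal-Wallis test".

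**The concern.** Stopping study treatment and stopping measurement are different decisions, and these clauses do not separate them. A patient who stops taking capsules or exercising can usually still complete a questionnaire. If such a patient is removed from the study, the Day 57 score is not collected, the primary test loses an observation, and the remaining patients are those who were not removed for poor adherence. The estimate then describes that subset, not everyone randomised.

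The behaviour that can trigger removal is also what the feasibility criterion measures. If the analysis dropped removed patients, adherence would look better because poor adherers had left. Section 8 does not say how pills, sessions and minutes after a removal are counted.

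**Working it through.** **1. The plan's own figure.** Inputs from Section 8: difference 9.5 − 3 = 6.5, SD 10, two-sided alpha 0.10, 30 per arm. The noncentrality is 6.5/(10·√(2/30)) = 2.517, with 58 degrees of freedom and critical t 1.672. Power is 80.0%, as stated. For dropout, 30/0.95 = 31.6, so 32 per arm and 96 in all. The margin is 32 − 30 = 2 patients per arm for every cause of loss.

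**2. Power by number of Day 57 scores** (same formula, n per arm):

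| Scores per arm | Lost of 32 | Power |
|---|---|---|
| 32 | 0 | 82.3% |
| 30 | 2 | 80.0% |
| 29 | 3 | 78.8% |
| 27 | 5 | 76.2% |
| 24 | 8 | 71.7% |

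**3. What keeping non-adherent patients would do.** Assume k of 32 per arm are non-adherent and keep a fraction f of the effect. With p = k/32, the difference is 6.5·(1 − p + f·p). The treated-arm variance is 100 + p(1 − p)·(6.5(1 − f))², and the control variance is 100. For k = 3 and f = 0, the difference is 5.89 and the treated-arm SD 10.18.

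| k per arm | Removed | Kept, f = 0 | Kept, f = 0.5 | Kept, f = 1 |
|---|---|---|---|---|
| 3 | 78.8% | 74.7% | 78.8% | 82.3% |
| 5 | 76.2% | 69.0% | 76.4% | 82.3% |
| 8 | 71.7% | 59.8% | 72.4% | 82.3% |

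Keeping and removing give equal power at f = 0.50, 0.49 and 0.47 respectively.

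**4. Feasibility (secondary; every adherence value is assumed).** The adherence table cited in Section 1.4 was not available in the text reviewed. Take 32 patients in the combination arm, 29 completers at 80%, and 3 who stop after week 2 having done 80% until then. Over the full course those 3 score 80·2/8 = 20%. The mean is 80% in completers and (29·80 + 3·20)/32 = 74.4% in all randomised. If they stop after week 3 they score 30%, the mean is (29·80 + 3·30)/32 = 75.3%, and the verdict does not change.

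Smallest k for which ((32 − k)·C + k·W)/32 falls below 75, where C is completers' and W removed patients' mean adherence:

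| C | W = 0 | W = 20 | W = 40 | W = 60 |
|---|---|---|---|---|
| 78 | 2 | 2 | 3 | 6 |
| 80 | 3 | 3 | 5 | 9 |
| 85 | 4 | 5 | 8 | 13 |
| 90 | 6 | 7 | 10 | 17 |

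Walking needs its own rule, because the prescription is reviewed weekly and a removed patient has no later one. Assume prescriptions rise in equal steps from 60 to 150 minutes over 8 weeks, with a stop after week 2 and 80% done until then, so 0.8·(60 + 72.9) = 106.3 minutes. Adherence is 80% if only weeks 1–2 count, 106.3/570 = 18.6% with the week-2 prescription carried on, 106.3/840 = 12.7% on the rising schedule, and 10.3% if the later weeks are set at 150 minutes. Whether later weeks count matters far more than which rule fills them.

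**The case against.** Much can be said for the plan. The clause is permissive, nothing forbids a Day 57 questionnaire after removal, and the definition covering procedures sits on the mandatory list only. Patients removed for missing visits might have given no Day 57 score anyway. Multiple imputation is available, and the repeated-measures analysis can use earlier scores. Removals would be visible, since reasons are recorded and the proportion completing is estimated. The power loss is small, and keeping patients who no longer benefit can cost more power than removing them.

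All of this stands as mitigation, but it does not close the gap. Imputation is optional and unspecified, the repeated-measures analysis is not the primary test, and recording a reason does not recover a score. The dilution argument concerns power only; removal buys that power by changing which patients the estimate describes.

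Three stronger readings are tempting and are not supported. A reader might infer that scores will certainly be lost; the discretion makes this possible, not certain. A reader might infer bias between the two compared arms. The documents do not show it: both arms have the same physical activity and identical capsules, in a phase described as double-blind. A reader might infer that the feasibility criterion is undefined. Its wording (total prescribed amounts, all patients for pills, the 8-week intervention) already leans towards a full-course denominator, and low adherence before removal enters any calculation that includes the patient.

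**Conclusion.** The concern holds as a design weakness that should be corrected, though it is not fatal. As written, discretionary removal for non-compliance can end participation, and no section keeps the primary assessment going. Beyond about 2 losses per arm from all causes, power falls below the planned 80%, to 78.8% with 3 lost and 71.7% with 8. The documents give no expected rate of such removals, so these figures show sensitivity and are not forecasts. The power figures rest on the plan's own difference, SD and alpha; the dilution figures rest on assumed retained effects.

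The feasibility part is minor. The verdict is sensitive to few removals only if completers average not far above 75%; with completers at 90%, 6 to 17 of 32 removals would be needed across the assumed range.

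**What to change.** 1. In Section 5.2.1 and the Treatment compliance paragraph, state that non-compliance alone does not end outcome assessment. Seek the Day 57 FACIT-F from every randomised patient except those who have withdrawn consent or fall under the mandatory list in Section 5.2.1. Allow it by telephone: Table 4 already does so at Days 15 and 43 but not at Day 57, and Section 7.2.6 foresees telephone questionnaires. Include these scores in the primary comparison by assigned arm.
2. For the 75% criterion, keep the threshold and use the full 8-week denominator in all patients randomised to the combination arm. Count pills and strength sessions after a non-compliance stop as not done. State one rule for walking minutes, for example the last assigned weekly prescription carried on. Say whether deaths and disease-related withdrawals stay in the denominator, and report them separately.
3. Limit the three-arm adherence comparison to pills, because Section 6.1 assigns controls stretching only.
4. The sponsor must reconcile the anti-cancer-therapy wording in Section 5.2.1 with Section 6.7, which disallows systemic antitumor therapy, and with the Synopsis Background, which describes most such patients as on active therapy. This affects how many patients the removal clause can reach. No clinical rule is proposed here.

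The cost is a few sentences, a few telephone questionnaires, some Day 57 scores taken in a different mode, a possibly less favourable adherence figure, and the dilution shown above if kept patients retain less than about half the effect.
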